## **SECTION 7 STATISTICAL CONSIDERATIONS AND ANALYSIS**

Our primary outcome is the difference in change in glycemic variability in those randomized to LCSB restriction compared to controls, calculated as difference in average daily TIR in Weeks 11 and 12 compared to Weeks -1 and 0. Because no prior study has assessed glycemic variability before and after LCSB restriction, we have powered our study using changes before and after LCS consumption. Suez et al., reported a  $1564 \pm 1852$  (mg·dL·120 mins) $^{-1}$  increase in glucose AUC post-LCS versus baseline, in 7 volunteers consuming saccharin (equivalent to 4-5 diet sodas per day) for 1 week. Using a similar effect size, 13 subjects per group will provide 80% power to detect differences in glycemic control before and after LCS restriction versus control (G\*Power; V3). Because 60% (4 of 7) of participants were considered LCS-responders by Suez, we will randomize 20 participants to the intervention and control, respectively (n=40). 48 subjects (24 per group) will account for 20% attrition. However, because prior studies conducted by Drs. [name] and [name] in this patient population have generated 70-80% usable CGM data, we will conservatively enroll 60 subjects (n=30 per group). We will use 1:1 block randomization stratified by LCSB type (sucralose or aspartame + ace-K) to lay the groundwork for evaluating potential differences in effects of sucralose versus aspartame in future studies.

Univariate analyses will be performed using an intention to treat approach. The maximum number of days of glycemic data will be used without imputations for missingness. Bivariate associations will be examined using cross tabulations, odds ratios, and chi-squared tests; boxplots, mean differences, and ANOVA, and correlations, as appropriate. We will identify and validate outliers and non-parametric tests will be used in the case of non-normal data. By establishing strengths of crude associations and highlighting irregular data, descriptive analyses will be a reference for more complex models. Changes in glycemic variability and other metabolic outcomes pre/post intervention will be compared between the groups using ANOVA. Hypothesis

testing will be two-sided with a type I error of 0.05. Analyses will be summarized using regression estimates, p-values, and 95% CI and performed using SAS 9.4.

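### With 20% attrition followed by 70-80% usable CGM data, 30 enrolled per group leaves 17-19 evaluable, short of the plan's own 20, so the enrolment figure is not conservative

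*Combined protocol and SAP*

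**What the plan says.** The whole calculation is in Section 7 (Statistical Considerations and Analysis) and runs in four steps.

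1. Base size: "13 subjects per group will provide 80% power to detect differences in glycemic control before and after LCS restriction versus control".
2. Responder allowance: "Because 60% (4 of 7) of participants were considered LCS-responders", the plan goes to 20 per group: "we will randomize 20 participants to the intervention and control, respectively (n=40".
3. Attrition: "48 subjects (24 per group) will account for 20% attrition".
4. CGM loss: earlier studies "in this patient population have generated 70-80% usable CGM data", so "we will conservatively enroll 60 subjects (n=30 per group".

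The CGM step is introduced as a further loss on top of attrition. The same section defines the primary outcome as a change in average daily time in range (TIR) between two CGM windows, Weeks -1 and 0 and Weeks 11 and 12. It says that missing glycemic data will not be imputed. The Protocol Summary sets the accrual ceiling for the RCT at 60 children.

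**The concern.** A reader of Section 7 will take 60 as a number with some margin over the 40 evaluable children the plan aims for. On the plan's own loss rates there is no margin. The attrition step multiplies by 1.2 where it should divide by 0.8, and the CGM step is sized for the better end of the quoted range. Each shortfall is small, but they act in the same direction and compound.

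The consequence is that the trial would probably be analysed on fewer children than the plan says it needs. With no imputation, a child with no usable CGM data in either window has no change score. With accrual capped at 60, the gap cannot be closed by enrolling more. The plan also does not say how many evaluable children it expects, or what difference in TIR change that number can detect.

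**Working it through.** **Inputs (all from Section 7):** target 20 per group; attrition 20%; usable CGM data 70-80%; enrolment 30 per group; two-sided 5% level ("testing will be two-sided with a type I error of 0.05").

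**Reproducing the plan's figure.**
- Attrition: 20 x 1.2 = 24.
- CGM: 24/0.80 = 30.

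So 30 is obtained exactly, but only by multiplying by 1.2 and using the 80% rate.

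**Correct inflation.** To keep n evaluable after losing a fraction a, enrol n/(1 - a).
- Attrition: 20/0.8 = 25. Check: 24 x 0.8 = 19.2, below 20.
- CGM step from the plan's 24: 24/0.8 = 30, but 24/0.7 = 34.3.
- Both losses from 20: 20/(0.8 x 0.8) = 31.25, so 32 per group; 20/(0.8 x 0.7) = 35.7, so 36 per group.

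**Forward check on 30 enrolled per group, 20% attrition first:**

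| Usable CGM | Evaluable per group | Total of 60 | Short of 20 per group |
|---|---|---|---|
| 80% | 30 x 0.8 x 0.80 = 19.2 | 38.4 | 0.8 |
| 75% | 30 x 0.8 x 0.75 = 18.0 | 36.0 | 2.0 |
| 70% | 30 x 0.8 x 0.70 = 16.8 | 33.6 | 3.2 |

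The result is below 20 across the whole quoted range: about 17-19 per group, 34-38 in total.

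**Alternative reading.** If the 70-80% already counts dropouts, only one loss applies: 30 x 0.7 = 21 to 30 x 0.8 = 24. The target is then met.

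**Detectable difference.** For a two-sample t-test, two-sided 5%, 80% power (noncentral t), the standardised difference in change that can be detected is:
- 17 per group: 0.99 SD
- 19 per group: 0.93 SD
- 20 per group (target met): 0.91 SD
- 21-24 per group (alternative reading): 0.89-0.83 SD

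These are in units of the SD of TIR change, which the plan does not give, so they cannot be turned into percentage points of TIR from the documents.

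**What the shortfall costs in power.** As an illustration, take the effect size the plan quotes, 1564/1852 = 0.84 SD, in a two-sample t-test, assuming that SD holds in both groups. Power is 74% at 20 per group, 72% at 19 and 67% at 17. Falling short of 20 therefore costs about 2 to 7 percentage points.

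**The case against.** **The loss rates may not be successive.** Section 7 does not say whether 70-80% usable is a share of children or of CGM days, or whether it already counts dropouts in those earlier studies. If dropouts are counted, 30 per group is enough. If it is a share of days, a child with some missing days may still contribute, since the plan uses as many days of glycemic data as it has. This stands as a real uncertainty. It does not rescue the text, because the plan's own move from 24 to 30 treats the CGM loss as coming on top of attrition. Correcting 24 to 25 is needed on any reading.

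**The gap is small.** At 80% usable it is less than one child per group. That is fair: the shortfall becomes material only toward 70%, a rate the plan itself quotes. This is also a pilot, with feasibility among its aims.

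**A reader might infer that these losses make the 80% power statement wrong.** The documents do not support that. The plan attaches 80% power to 13 per group and states none for 20 or 30, and 17-19 exceeds 13. Even a fully met target of 20 gives only 74% in a two-sample test at 0.84 SD, so most of the gap to 80% has another cause. The figure of 13 fits a paired pre/post test (79.8% power at 0.84 SD), whereas a two-sample test with 13 per group has 54%. That mismatch with the between-group primary comparison is a separate point.

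**A reader might also want 20 corrected to 22-23,** since 13/0.6 = 21.7 and 13/(4/7) = 22.75. That is not a sound correction. The quoted effect is an "increase in glucose AUC post-LCS versus baseline, in 7 volunteers consuming saccharin", so it already averages over responders and non-responders, and dividing by the responder fraction is not clearly required.

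**Conclusion.** The point holds as an inflation shortfall. The attrition step should give 25 per group, not 24. Thirty per group is reached only with the best-case CGM rate, and both stated losses together leave 16.8-19.2 evaluable per group against the plan's 20. The word *conservatively* is therefore unsupported as written.

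This rests on two assumptions: that the losses are successive, which the plan's own sequence implies, and that usable is a share of children, which the plan does not state. If the 70-80% rate already includes dropouts, the enrolment is adequate and only the attrition step and the missing definition need correcting. The finding concerns the stated evaluable size and the absence of a matching detectable difference. It does not overturn the 80% power claim at 13 per group.

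**What to change.** Keep 60 enrolled and revise Section 7 as follows.

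- Correct the attrition step from 24 to 25 per group (50 in total).
- Say what 70-80% usable counts: children or days, and with or without dropouts.
- State the expected evaluable number. On the successive reading this is about 34-38 in total (17-19 per group). If dropouts are already included, it is 42-48 (21-24 per group).
- Delete *conservatively*. Present 60 as the enrolment chosen, with what it is expected to deliver, because it does not follow from 25 at either CGM rate (25/0.8 = 31.25; 25/0.7 = 35.7).
- State the between-group difference in TIR change detectable with 80% power at two-sided 5%: about 0.93-0.99 SD at 17-19 per group, with the assumed SD of TIR change so that it can be read in TIR units.

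The cost is wording only, with no extra children or procedures. The one downside is that the stated evaluable size and detectable difference become less favourable.

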
Outcome Measures:
	
HbA1c, CRP, IL-6, TNF-<math>\alpha</math>, LDL, HDL, triglycerides, and free fatty acids (FFA) measured in blood samples. Sucralose and ace-K concentrations in biological fluids, including urine. Visceral fat area from DXA or BodPod. Continuous blood glucose to assess glycemic variability, photo-assisted food records to assess adherence to LCSB restriction and any changes in diet throughout study, beverage log to assess adherence, satisfaction survey, Diabetes Self-Care Inventory (SCI), physical activity questionnaire (PROMIS), COVID-19 diabetes management questionnaire, Eating Attitudes (EAT) questionnaire, and an in-depth interview. Additional, in-depth interview about COVID-19 impacts on T1D management (for those who screen ineligible for full study and those who participate in DRINK and are interested in also participating in this additional interview)

Study Intervention/ Procedures:
	
Children will be randomly assigned to either replace their LCSB consumption with still or seltzer water or to continue their usual LCSB consumption for 12 weeks. Parents who participate in the COVID-19 interviews will undergo a brief qualitative interview with a trained interviewer.

Statistical Analysis:
	
Univariate analyses and one-way ANOVA will be used to assess group differences in glycemic variability and other metabolic outcomes pre/post intervention. Bivariate associations will be examined using odds ratios, chi-squared, boxplots, mean differences, and ANOVA, as appropriate. Qualitative data collected during interviews will be transcribed verbatim and thematically coded.

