Eligible participants will be scheduled for a baseline visit in the Clinical Research Unit (CRU) at CNMC. One group will replace their usual LCSB consumption with unsweetened still or seltzer water (LCSB restriction) for 12 weeks. The other group will continue their usual LCSB use (control) for 12 weeks. The baseline visit will take place in the CRU, where height and weight will be measured, a spot urine sample will be collected (for measurements of sucralose and ace-k concentrations), and a blood draw will be performed. Participants will be provided with a copy of their laboratory (blood) results from the baseline visit and will be encouraged to discuss them with their physician. Participants will have *the DEXCOM G6™ sensor removed* and CGM data downloaded. In a subset of participants (n=30), a DXA scan or BodPod will also be performed, as R21 budget constraints preclude DXA or BodPod on all 60 subjects.

*Subjects will be randomized to either: 1) LCSB restriction or 2) continuation of usual LCSB intake (control).* All participants (both LCSB restriction group and control group) and their parent(s) or guardian(s) will undergo a brief, 20-minute orientation where the PI and study dietitian will provide an introduction to the study, instructions on completing food records, *education on CGM and placement of the DEXCOM G6™ sensor*, and counseling on healthy eating strategies. For children not already using CGM, parents will also receive 3 additional sensors (replacement in Week 1, placement in Week 11, and replacement in Week 12 for 14 days wear time), written instructions and additional resources (YouTube video) for placing (or replacing) the glucose sensors. Participants in the intervention group will be counseled on avoiding LCSBs. Participants and their parent will also be given a brochure (enclosed) on avoiding LCSs to take home which will include a list of specific foods and beverages containing LCSs to avoid during the study. Parents will also receive information on strategies to encourage study adherence (enclosed). Participants in the control group will be counseled on healthy eating as those in the intervention group (in accordance with standard dietary guidance for T1D management), with the exception of information and resources for avoiding LCSBs. Participants in both groups will be provided with sample beverages (LCSBs or unsweetened still and seltzer water), per their randomization.

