Table 1. Timing of Study Procedures			
Time-point	Location	Assessments	Procedures
Interview about COVID-19 impacts on T1D management (separate from rest of trial)	Home	Qualitative interview	Consent, questionnaire, qualitative interview
Screening Visit	Clinic or Home	Eligibility Determination, Enrollment, Questionnaires	Screener, consent, assent, EAT, self-care (SCI), COVID-19 questionnaire, PROMIS questionnaire
Week 0	Home	Diet assessment, glycemic variability	Food record, CGM, beverage log
Baseline Visit	CRU	Glycemic control (HbA1c), lipids, inflammation, visceral adiposity, anthropometrics	Height/weight, spot urine, blood draw, CGM download, DXA or BodPod (subset)
Weeks 1-5	Home	Adherence	Food record, beverage log
Week 6	Home	Diet assessment, adherence, intervention booster	Food record, beverage log, spot urine
Week 7-10	Home	Adherence	Beverage log
Week 11-12	Home	Diet assessment, glycemic variability, adherence	Food record, CGM, beverage log
Follow-up Visit	CRU	Glycemic control (HbA1c), lipids, inflammation, visceral adiposity, anthropometrics, acceptability, feasibility	Height/weight, spot urine, blood draw, SCI, satisfaction survey, qualitative interview, CGM download (for weeks 11 and 12), DXA or BodPod

Laboratory analyses: All blood assays will be run by LabCorps. Urine analyses will be performed by the Clinical Mass Spectrometry Laboratory at the National Institutes of Health. Blood and urine samples will be shipped by certified personnel in the CTSI-CN PCI at Children's National.

Additional blood and urine specimens will be stored in the CTSI-CN PCI at Children's National for up to three years after completion of data collection for future analyses. All samples will be stored deidentified. Depending on the future analyses performed, deidentified samples may be shipped to external commercial or academic laboratories in the future.

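### The between-arm test is one-way ANOVA on change scores; ANCOVA on baseline and the LCSB-type stratum answers the same question, usually more precisely, at almost no cost

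*Combined protocol and SAP*

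**What the plan says.** Section 7 defines the primary outcome as the between-arm difference in change in average daily TIR, Weeks 11 and 12 against Weeks -1 and 0. It gives one between-group test: "Changes in glycemic variability and other metabolic outcomes pre/post intervention will be compared between the groups using ANOVA". The Protocol Summary agrees: "Univariate analyses and one-way ANOVA will be used to assess group differences in glycemic variability and other metabolic outcomes pre/post intervention".

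On allocation, Section 7 says "We will use 1:1 block randomization stratified by LCSB type (sucralose or aspartame + ace-K"). The stated reason is groundwork for later studies of the two sweetener types. No analysis text uses LCSB type as a model term.

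Section 7 also refers to more complex models and to reporting regression estimates, but lists no covariates and no model. For distributional problems it says: "We will identify and validate outliers and non-parametric tests will be used in the case of non-normal data".

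Baseline and follow-up values are already scheduled. CGM is worn in the run-in and in Weeks 11-12. Table 1 in Section 6.4 lists the same assessments at the baseline and follow-up visits: "Glycemic control (HbA1c), lipids, inflammation, visceral adiposity, anthropometrics". Section 4 limits the adiposity measurement: "In a subset of participants (n=30), a DXA scan or BodPod will also be performed".

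**The concern.** One-way ANOVA with two arms is the two-sample t-test applied to follow-up minus baseline. Subtraction is the right adjustment only if the regression slope of follow-up on baseline is 1. With similar spread at the two times that slope equals rho, which is below 1, so subtraction over-corrects and adds noise. ANCOVA estimates the slope from the data. Under randomization both methods target the same between-arm difference.

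The stratification factor is a separate, smaller matter. An analysis should normally follow the randomization. Leaving out a stratum makes the standard error too wide only if the stratum is prognostic, and the documents do not say whether LCSB type is.

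At stake is the width of the confidence intervals. Section 6.4 describes the trial as generating preliminary evidence, so interval width is one of its main products, and the accrual ceiling of 60 children means precision cannot be bought with more enrolment.

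**Working it through.** **Inputs from Section 7.** "testing will be two-sided with a type I error of 0.05". Effect size from the cited saccharin study: d = 1564/1852 = 0.844, a mean change over its SD for glucose AUC in 7 volunteers. Enrolment is 30 per arm, attrition 20%, usable CGM data 70-80%.

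**Assumed.** Rho is not given; I use 0.5, 0.7, 0.8 and 0.9, with equal SDs at the two times. Applying d to TIR is illustration only.

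**The plan's own figure.** Section 7 states that "13 subjects per group will provide 80% power to detect differences in glycemic control before and after LCS restriction versus control". A one-sample (paired) t-test at d = 0.844 gives 79.8% power at n = 13, so the figure reproduces as a within-group calculation. As a two-sample comparison of changes, 13 per arm gives 54% and 24 per arm are needed for 80%. That is a separate point, but it is why power below uses the two-sample form.

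**Evaluable children per arm.**
- CGM outcome: 30 x 0.8 x 0.8 = 19.2 (19), or 30 x 0.8 x 0.7 = 16.8 (17). Multiplying the two losses is an assumption.
- Blood outcomes: 30 x 0.8 = 24.
- Adiposity subset of 30: 15 x 0.8 = 12, assuming an even split and the same attrition.

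**Variance ratio.** With common SD s, the change score has variance 2s²(1 - rho) and the ANCOVA residual has s²(1 - rho²). The ratio is (1 - rho²)/(2(1 - rho)) = (1 + rho)/2, giving 0.75, 0.85, 0.90 and 0.95.

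**Covariate cost.** With n per arm, multiply by 1 + 1/(2n - 5) for estimating the slope, and use 2n - 4 degrees of freedom instead of 2n - 2. Example at n = 19, rho = 0.7:
- variance ratio: 0.85 x (1 + 1/33) = 0.876
- square root: 0.936
- ratio of t quantiles (34 against 36 df): 2.032/2.028 = 1.002
- interval-width ratio: 0.936 x 1.002 = 0.938

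Across the four values of rho at n = 19, the width ratios are 0.881, 0.938, 0.965 and 0.991.

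**Power.** Noncentral t with noncentrality d x sqrt(n/2) for the change score. For ANCOVA, d is first divided by sqrt{[(1 + rho)/2] x [1 + 1/(2n - 5)]}.

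| Per arm | Change score | rho 0.5 | rho 0.7 | rho 0.8 | rho 0.9 | Break-even rho |
|---|---|---|---|---|---|---|
| 19 (CGM) | 71.7% | 82.0% | 77.1% | 74.7% | 72.4% | 0.935 |
| 17 (CGM) | 66.6% | 77.2% | 71.9% | 69.5% | 67.1% | 0.925 |
| 24 (blood) | 81.7% | 90.4% | 86.6% | 84.6% | 82.7% | 0.951 |
| 12 (adiposity) | 50.7% | 60.1% | 54.8% | 52.5% | 50.4% | 0.883 |

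In sample-size terms, 19 per arm under ANCOVA is worth about 19/0.876 = 22 per arm under change scores at rho 0.7. At rho 0.5 the variance ratio is 0.75 x (1 + 1/33) = 0.773, and 19/0.773 = 25.

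**Simulation checks.** At 20 per arm both methods showed essentially no bias, and at rho 0.7 type I error was 0.047 for change scores and 0.047 for ANCOVA with baseline and stratum. Adding a non-prognostic stratum term moved power by at most 0.2 points. If LCSB type shifted the outcome by 0.5 SD of change (assumed), power at rho 0.7 was 72% for change scores, 77% with baseline, and 79% with baseline and stratum.

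**Unequal SDs.** For follow-up/baseline SD ratios from 0.8 to 1.25, the large-sample variance ratio never exceeded 1. It reaches 1 when the true slope is 1, for example SD ratio 1.25 with rho 0.8 (1.25 x 0.8 = 1).

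**The case against.** The strongest reply is that this is an efficiency preference. The planned test is valid, it matches an outcome defined as a difference in change, and the trial is a pilot. The gain depends on a correlation nobody has stated: the 10-point rise in power occurs only at rho 0.5, and at rho 0.9 there is practically none. At 12 per arm and rho 0.9, ANCOVA is marginally worse (50.4% against 50.7%). All of this stands, and it is why the point is a recommendation and not a claim of error.

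The covariate cost above is also slightly optimistic, because it treats the stratum as balanced among the children analysed, whereas blocks balance only those randomized. Simulating 60 randomized children with 64% retained at random gave width ratios of 0.889, 0.944, 0.971 and 0.997. The extra cost is real but under one percentage point, and the direction does not change. In a single trial the ANCOVA interval was the wider one about a third of the time at rho 0.8 and about half the time at 0.9; the advantage is an average one.

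The usable-CGM percentage may refer to days and not children, in which case 17-19 per arm is too low. At the plan's own target of 20 per arm the picture is much the same: about 74% for change scores, against 84%, 80%, 78% and 75% for ANCOVA.

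The references to more complex models and regression estimates do not close the gap, since they name no terms. Three details do need care in the fix: logged outcomes give a ratio and not a difference in change, adiposity may be measured by DXA or BodPod, and the eligibility screener lets a child report both sweetener types.

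**Conclusion.** The concern holds. Change-score ANOVA is the only between-group test specified, and it uses neither an estimated baseline slope nor the stratification factor. For outcomes analysed on their original scale, ANCOVA estimates the same between-arm contrast. At 17 to 24 children per arm its interval is roughly 12% narrower at rho 0.5, shrinking to about 1% at rho 0.9, and the gain vanishes at rho of about 0.93 to 0.95. In the adiposity subset it vanishes at about 0.88. These figures assume equal SDs at the two times and, for power, the borrowed effect size. The effect of omitting LCSB type cannot be quantified from the documents; the case for including it is consistency with the randomization. Nothing here biases the estimate or invalidates a conclusion. The change should be made because it is nearly free, and it should be made before the data are analysed so that the choice of covariates cannot look data-driven.

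**What to change.** Replace ANOVA of change in Section 7 and in the Protocol Summary with wording such as:

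> The primary analysis is an ANCOVA of mean daily TIR in Weeks 11-12 on arm, mean daily TIR in Weeks -1 and 0, and the LCSB-type stratum used at randomization. The adjusted between-arm difference is reported with its 95% CI. Unadjusted change-score ANOVA is a sensitivity analysis.

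Then:

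- Use the same model for HbA1c, lipids, cytokines and adiposity, regressing the follow-up visit value on the baseline visit value.
- Name in advance the outcomes to be analysed on the log scale at both times (for example CRP, IL-6 and TNF-alpha), and say that their contrast is a ratio.
- Limit the existing non-parametric rule to outcomes still non-normal after that, and name a rank-based test that keeps baseline and stratum.
- Note that only 30 children have adiposity measured, so little or no gain is expected there if rho is about 0.88 or more. State how DXA and BodPod values will be handled.
- Reconcile Section 4, which mentions random placement in the screening text and again at the baseline visit, so that it is clear the baseline CGM period precedes allocation.

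The cost is this wording and two degrees of freedom, one for baseline and one for a two-level stratum. No new data are needed.
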